18.1.6. Overall Summary of Adverse Events

In addition to the summaries above, an overview of TEAEs will be summarized (not broken down by SOC or PT) by number and frequency of subjects and by number of AEs:

- Any TEAE
- Any related TEAE*
- Any serious TEAEs
- Any related serious TEAEs*
- TEAEs leading to death
 - Liver-related TEAEs leading to death
- TEAEs leading to study treatment discontinuation
 - Related TEAEs leading to study treatment discontinuation*
 - Liver-related TEAEs leading to study treatment discontinuation
- TEAEs leading to study treatment interruption
 - Related TEAEs leading to study treatment interruption*
- TEAEs by maximum severity
- Related TEAEs by maximum severity*
- TEAEs by relationship to study treatment

* “Related TEAEs” refers to TEAEs related or probably related to study treatment or are missing relationship.

Comparative analyses will be performed for:

- Deaths
- Serious TEAEs
- TEAEs leading to study treatment discontinuation
- TEAEs of special interest
- Serious infections
- Opportunistic infections (Narrow)
- Malignancies

Risk differences between etrasimod and placebo along with 95% CIs using the Wilson’s score method will be presented.

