At the end of the 12-Week Treatment Period, subjects will undergo Week 12 efficacy and safety assessments and be evaluated for clinical response/remission as well as UC disease worsening. Subjects whose UC condition in the opinion of the Investigator has not improved or has worsened, compared with Baseline (Week 0/Day 1), as defined in Clinical Study Protocol APD334-301 Section 5.1.1 and who meet other eligibility criteria will have the option to enter an open-label extension (OLE) study (Study APD334-303). Subjects must complete Week 12 to be eligible for the OLE. Subjects who do not meet disease worsening criteria, including those demonstrating clinical response/remission at Week 12 will continue into the 40-Week Treatment Period and continue their double-blind treatment. Subjects who either experience disease worsening in the 40-Week Treatment Period or complete all study procedures at Week 52 will have the option to enroll into the OLE study if they meet all eligibility criteria. Subjects who do not participate in the OLE study will have 2-Week and 4-Week Follow-Up visits after their last treatment administration/Early Termination (ET) visit. The study design is outlined in [Figure 1](#).

Figure 1: Study Design

JAK, Janus kinase; UC, ulcerative colitis

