16.1.4.1. Multiple Imputation Under MAR

Any missing component scores of MMS at the planned assessments will be imputed using multiple imputation under MAR. MAR assumes the missing value is independent of unobserved outcomes given observed data (eg, subjects with missing RB subscores can be modeled based on subjects with observed RB subscores) (Rubin 1987).

The following steps will be implemented:

Step 1

Regardless of the arbitrary missing data pattern (ie, non-monotone or monotone), a fully conditional specification (FCS) method with predictive mean matching for continuous variables will be used to impute the missing data at all timepoints. The FCS method allows for separate conditional distributions for each imputed variable. The predictive mean matching approach creates a regression model using parameters sampled from the posterior distribution and then a predicted value for each missing value is computed. The missing value is replaced by randomly selecting an observation from a set of 'k' values that are the closest predicted values to the missing predicted value. Missing data imputation will be performed using the SAS PROC MI procedure. The number of imputations will be 40 and is based on a projected overall dropout rate of 50% and relative efficiency of ~ 99%. A separate imputation model will be used for each treatment group. The RB subscore, SF subscore, ES, PGA, stratification variables, a binary variable indicating if a subject is a prior UC treatment failure of oral 5-ASA only (ie, subject had an inadequate response, loss of response, or intolerance to previous treatment with oral 5-ASA and did not have an inadequate response, loss of response, or intolerance to any other previous UC medication), Geboes index score, and biomarker measurements (absolute lymphocyte count [ALC], fecal calprotectin [FCP], hs-CRP, log-transformed) at each planned visit will be included in the imputation models. Refer to [Appendix 3](#) for the order of variables and timepoints in the model.

Step 2

For each of the imputed datasets at Week 12 and Week 52, subjects will be classified as responder or nonresponder based on the criteria specified in Section 16. For each dataset, the proportion of responders will be calculated. For endpoints requiring MMS, MMS will be recomputed by summing the scores of ES, SF, and RB.

Step 3

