18.1.1. All TEAEs

All TEAEs will be summarized by SOC and PT. This summary table and all other TEAE summaries by SOC and PT will be presented by descending frequency in the etrasimod group. All AEs, regardless of treatment-emergent status, will be included in an AE listing. Additionally, a listing of other AE details as collected on the CRF will be presented.

Exposure-adjusted incidence rate (EAIR) of TEAEs will be summarized by SOC and PT. Exposure is defined as the sum of either time (year) from first dose to the onset of first such event for those who experienced this AE, or time (year) from first dose to last participation for those who did not experience this AE. The EAIR is calculated as the number of subjects with the AE divided by the total exposure in subject-years.

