18.1.2. TEAEs Leading to Discontinuation of Study Treatment

TEAEs leading to discontinuation of study treatment will be identified by action taken being recorded as “Drug withdrawal” on the Adverse Events eCRF.

All TEAEs leading to discontinuation of study treatment will be summarized by SOC and PT. A listing of all TEAEs leading to discontinuation of study treatment will also be presented.

Time to study treatment discontinuation due to liver-related AE will be summarized for the Safety Set for subjects who had such an event reported during the study. Descriptive statistics, Kaplan-Meier estimate of 25th, 50th, and 75th percentile time to event, 95% CIs, and p-value from the log rank test will be displayed. If a subject did not have the event, they will be censored at the date of last dose. If the date of last dose is missing, the date of last study visit up to Week 52 will be used. If no event is ever observed, then summary will not be generated.

Liver-related AEs are defined by either SOC of hepatobiliary disorders or PT of alanine aminotransferase abnormal, alanine aminotransferase increased, aspartate aminotransferase abnormal, aspartate aminotransferase increased, hepatic enzyme abnormal, hepatic enzyme increased, liver function test abnormal, liver function test increased, transaminases abnormal, or transaminases increased.

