18.1.4. TEAEs Leading to Death

TEAEs leading to Death are those events which are recorded with an outcome as “Fatal” on the Adverse Events eCRF. A listing of TEAEs leading to death will be presented.

Time to death due to liver-related AE will be summarized for the Safety Set for subjects who had such an event reported during the study. Descriptive statistics, Kaplan-Meier estimate of 25th, 50th, and 75th percentile time to event, 95% CIs, and p-value from the log-rank test will be displayed. If a subject did not have the event, they will be censored at the date of last dose. If the date of last dose is missing, the date of last study visit up to Week 52 will be used. If no event is observed, then the summary will not be generated.

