18.1.5. TEAEs of Special Interest

Categories of Targeted Medical Events (TMEs) and a list of preferred terms associated with these TME categories were developed based on the mechanism of action of etrasimod, prior experience with other agents acting via a similar mechanism, and disease-specific clinical judgment. In addition, where standard testing has been implemented to screen for potential AESI (eg, electrocardiograms, spirometry, serum transaminases, etc.), the relevant data will be reviewed to identify potential cases of AESI that investigators may not have identified and to provide quantitative data for AESIs. The proposed candidate terms will be reviewed to identify which events reflect AESI.

TEAEs of special interest will be summarized by category, subcategory, and PT by descending frequency by treatment group. Categories and subcategories of TEAEs of special interest are the following:

- Cardiovascular Events
 - Bradycardia
 - AV conduction delay
 - Hypertension
- Macular Edema
- Pulmonary Disorders
 - Airflow obstruction (forced expiratory volume in 1 second [FEV₁], forced vital capacity [FVC])
 - Decrease gas exchange (diffusing capacity of the lungs for carbon monoxide [DLCO])
- Infections
 - Severe infections
 - Opportunistic infections (Narrow)
 - Herpes simplex and herpes zoster

- Liver Injury
 - Liver transaminases elevation
 - Bilirubin elevation
- Posterior Reversible Encephalopathy Syndrome (PRES)
- Malignancies

For each category, subcategory, and PT, model-based analysis will be performed to compare treatment effect between etrasimod and placebo. An extended Cox regression model will be used to handle recurring AEs (Cao 2011). The stratification variables, naïve to biologic or JAK inhibitor therapy status at study entry (Yes or No), Baseline corticosteroid use (Yes or No), and Baseline disease activity (MMS: 4 to 6 or 7 to 9), will be included in the model. A subject with K events contributes (K+1) observations to the input data set; here K might be 0. The k-th observation of the subject identifies the time interval from the start date of the (k-1)-th event, or time 0 (if k = 1), to the start date of the kth event, k = 1, ..., K. The (K+1)-th observation represents the time interval from the K-th event to the date of censorship, ie, the date of last dose or date of last study visit up to Week 52, whichever is later. Hazard ratios, 95% CIs, and p-values for treatment effect comparison will be presented.

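### For serious TEAEs and TEAEs leading to discontinuation, the only planned between-arm comparison is a crude risk difference, which misleads if placebo subjects leave earlier for the extension

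*SAP*

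**What the plan says.** SAP 18.1.6 names seven categories for comparative analysis: deaths, serious TEAEs, TEAEs leading to discontinuation of study treatment, TEAEs of special interest, serious infections, opportunistic infections (narrow) and malignancies. The one measure given is "Risk differences between etrasimod and placebo along with 95% CIs" by Wilson's score method.

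Time at risk is handled in other sections, for other groupings:

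- 18.1.1: "Exposure-adjusted incidence rate (EAIR) of TEAEs will be summarized by SOC and PT". The rate is defined ("The EAIR is calculated as the number of subjects with the AE divided by the total exposure in subject-years"), but no between-arm contrast is attached to it.
- 18.1.5: "An extended Cox regression model will be used to handle recurring AEs". It gives hazard ratios, 95% CIs and p-values for each special-interest category, subcategory and preferred term. These include severe infections, opportunistic infections and malignancies.
- 18.1.2: "Time to study treatment discontinuation due to liver-related AE will be summarized". 18.1.4: "Time to death due to liver-related AE will be summarized for the Safety Set". Both cover liver-related events only.

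On leaving the study, SAP 3.1 states "Subjects must complete Week 12 to be eligible for the OLE". From that visit, subjects of either arm who have not improved or have worsened may roll over (also Protocol 5.1.1). SAP 16.1.4.1 bases the number of imputations on a "projected overall dropout rate of 50" percent, with no split by arm.

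**The concern.** A crude proportion depends on the event rate and on how long subjects are observed. Here early exit is tied to efficacy. The design assumes etrasimod works better (clinical remission at Week 52 of 23.5% v 10.0%, SAP 7). If it does, more placebo subjects would be expected to leave after Week 12, and they would have less time in which to record an event. With identical hazards the crude difference would then lean towards harm on etrasimod. With a truly higher placebo hazard, for instance from disease-related serious events, it could hide a benefit.

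The safety objective (SAP 2.3) concerns long-term safety over up to 52 weeks. For all serious TEAEs and all TEAE discontinuations, the formal contrast addressing it makes no allowance for unequal time at risk.

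**Working it through.** **Figures in the plan.** The documents state no expected safety difference, so there is none to reproduce. Two inputs can be checked. For the arm sizes of 280 and 140, exact enumeration of the one-sided Fisher test gives 92.8% power at Week 52 (stated 93.4%) and 95.5% at Week 12 (stated 96%). For the 50% dropout, relative efficiency with 40 imputations is 1/(1 + 0.5/40) = 98.8%, which matches the stated value of about 99%.

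**Assumptions, none of them in the documents.**

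- The same constant hazard h in both arms: 0.05, 0.10 or 0.20 per year, and 0.003 for deaths.
- Dropout on etrasimod/placebo of 50/50, 45/60, 40/70 or 35/80%. At 2:1 each pools to 50%, e.g. (2×40 + 70)/3 = 50.
- Exits all at Week 12, uniform over Weeks 12-32, or uniform over Weeks 12-52. All other subjects stay 52 weeks.

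**Formula.** Crude risk = d × mean of [1 − exp(−ht)] over the exit times + (1 − d) × [1 − exp(−h)], with d the dropout proportion and t in years.

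**Example: h = 0.10, 40/70 dropout, all exits at Week 12.** 1 − exp(−0.10×12/52) = 2.28% and 1 − exp(−0.10) = 9.52%.

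- Etrasimod: 0.4×2.28 + 0.6×9.52 = 6.6%
- Placebo: 0.7×2.28 + 0.3×9.52 = 4.5%

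| Exits (40/70, h = 0.10) | Mean weeks, E / P | Crude risk, E / P | Difference (points) | Risk ratio | Chance that 95% CI lies wholly above 0 |
|---|---|---|---|---|---|
| All at Week 12 | 36 / 24 | 6.6% / 4.5% | +2.2 | 1.49 | 12% |
| Weeks 12-32 | 40 / 31 | 7.4% / 5.8% | +1.6 | 1.28 | 8% |
| Weeks 12-52 | 44 / 38 | 8.1% / 7.0% | +1.1 | 1.15 | 5% |

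The nominal value for the last column is 2.5%. As a single-trial illustration of the middle row, 21/280 v 8/140 gives +1.8 points, 95% CI −4.0 to +6.4.

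**Range.**

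- Equal dropout (50/50): difference 0.
- All unequal splits, h from 0.05 to 0.20: +0.3 to +6.1 points, risk ratio 1.07 to 1.89. The chance that the CI lies wholly above zero is 2% to 46% (3% to 22% for 40/70). The top end needs 80% of placebo to leave, all at Week 12, and h = 0.20. That is an extreme case.
- Deaths at 0.003 per year: +0.02 to +0.10 points, and the CI essentially never excludes zero.

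**Opposite direction.** With 40/70 dropout and an etrasimod hazard of 0.10, a true placebo:etrasimod hazard ratio of 1.51, 1.29 or 1.16 (for the three exit patterns in table order) gives a crude difference of exactly zero.

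**After adjustment.** In the middle row, expected time at risk to first event or exit is risk/h: 0.0736/0.10 = 0.736 years and 0.0575/0.10 = 0.575 years. The rates are 10.0 v 10.0 per 100 subject-years, difference 0.

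**Limit of the adjustment.** Suppose both arms have an identical 8% risk, all of it before Week 12, with mean exposures of 40 and 31 weeks. Ignoring the small loss of time after a first event, the rates are 8/(40/52) = 10.4 and 8/(31/52) = 13.4 per 100 subject-years. That is a false advantage for etrasimod, which the crude and Weeks 0-12 differences would not show.

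**The case against.** The crude Safety Set difference is a legitimate description of the trial as run. SAP 18 plans no statistical comparisons of safety data unless specified, and 18.1.6 attaches no p-value. SAP 14 summarises exposure, so an imbalance could be noticed. These points stand, but they do not supply an adjusted contrast.

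A reader might infer that the comparative safety analyses as a whole ignore time. They do not: the Cox model covers every special-interest category, and liver-related discontinuation and death have Kaplan-Meier and log-rank analyses. One loose end is that 18.1.6 says serious infections while 18.1.5 models severe infections.

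A reader might also infer that a false excess will appear. The documents do not support that. Exit is open to both arms, the 50% is pooled, and equal dropout gives no bias. Very short placebo exposure should not be presumed either: if exits average Week 22, a placebo mean of 26 weeks needs (52 − 26)/(52 − 22) = 87% dropout.

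Nor do the Phase 2 results in Protocol 3.2 point to equal constant hazards. SAEs were 0% on 2 mg v 11.1% on placebo, and TEAEs leading to discontinuation were 8.0% v 0%. If serious events are commoner on placebo, the likelier fault is a muted benefit. Discontinuations tied to the Day 1 and Day 2 cardiac monitoring precede any extension exit and are barely affected. This limits the size of the problem but leaves the gap for these classes.

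**Conclusion.** The concern holds in a narrow, conditional form. For serious TEAEs and TEAEs leading to discontinuation as classes, the SAP plans no between-arm comparison that accounts for time at risk, while early exit depends on efficacy. The same gap exists for deaths, but the distortion there is at most about 0.1 point at the assumed rate, so deaths do not carry the case.

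The plausible size is a point or two for an event rate near 0.10 per year with clearly unequal dropout, and nothing if dropout is equal. Every figure rests on assumed hazards, dropout splits and exit times. The direction under equal hazards rests on placebo exposure being the shorter. This is a worthwhile, inexpensive addition to the plan and does not invalidate the existing analyses.

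**What to change.** Keep the crude risk difference in 18.1.6. For serious TEAEs and TEAEs leading to discontinuation, and for serious infections if these differ from the severe infections modelled in 18.1.5, add:

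1. The risk difference with 95% CI for Weeks 0-12, before extension exit is possible, with a stated cut-off.
2. One exposure-adjusted contrast over the whole period: the EAIR difference with 95% CI, or a time-to-first-event analysis.
3. Exposure by arm in the same table.

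State one end of time at risk. The SAP now uses last participation (18.1.1), last dose (18.1.2 and 18.1.4) and the later of last dose or last study visit up to Week 52 (18.1.5). The TEAE definition in 18.1 has no upper limit, while Protocol 9.10.8.2.2 collects adverse events to 30 days after the last dose. The rule should cover subjects who roll over.

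The cost is new class-level time-to-first-event derivations from data already collected, since 18.1.1 derives time at risk per SOC and preferred term. Specify this before unblinding, because SAP 4.2 requires later additions to be reported as unplanned. The EAIR assumes a roughly constant hazard, and neither option removes informative censoring by disease worsening. The adjusted contrast should therefore be read beside the crude and Weeks 0-12 differences.

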18.2. Deaths

Information collected about death (eg, date of death, primary cause of death) will be presented in a data listing, as described in Section [18.1.4](#).

18.3. Laboratory Evaluations

No local laboratory assessments will be used in any summaries except for lipid panel and thyroid panel tests. No local laboratory assessments will be used to derive maximum/minimum/worst value. Local laboratory assessments will be listed.

18.3.1. Safety Laboratory Evaluations

Hematology, serum chemistry, coagulation, and urinalysis are analyzed and reported by central laboratory and sometimes by local laboratory. Results out of reference range are flagged by the performing laboratory (eg, low, high). A full list of laboratory assessments to be included in the outputs is included in Clinical Study Protocol APD334-301 Table 6.

In general, presentations will use SI units. Quantitative laboratory measurements reported as “< X” or “> X”, where X may be the lower limit of quantitation (LLQ) or the upper limit of quantitation (ULQ), respectively, will be converted to X for the purpose of quantitative summaries, but will be presented as recorded, ie, as “< X” or “> X” in the listings. For urinalysis, only pH and specific gravity are considered as quantitative tests. If local and central laboratory assessments are available from the same day, central laboratory assessments will be used in the summary as per Section [6.4](#).

The following summaries will be provided for laboratory data:

- Value and change from Baseline by visit (for hematology, serum chemistry, quantitative urinalysis [pH and specific gravity], and coagulation)

- Incidence of abnormal values according to laboratory reference ranges by visit
- Incidence of lymphocytes $< 0.2 \times 10^9/L$, $0.5 \times 10^9/L$, or neutrophils $< 0.5 \times 10^9/L$, $1 \times 10^9/L$ at end of treatment and anytime in the study
- Shift from end of treatment to each follow-up visit in incidence of lymphocytes in normal range and in incidence of lymphocytes of at least 80% percent of Baseline, by visit (2-Week Follow-Up, 4-Week Follow Up, and Last Follow-Up)
- Shift from Baseline to end of treatment according to laboratory reference range (for quantitative measurements and categorical measurements)
- Evaluation of drug-induced serious hepatotoxicity (eDISH) plots for the following laboratory assessments (using values after the first administration of study treatment):
 - Maximum aspartate aminotransferase (AST) versus same-day total bilirubin
 - Maximum alanine aminotransferase (ALT) versus same-day total bilirubin
 - Maximum gamma-glutamyl transferase (GGT) versus same-day total bilirubin
 - Maximum alkaline phosphatase (ALP) versus same-day total bilirubin

The eDISH plots above will be repeated with adjustment for elevated Baseline.

- Incidence of hepatic enzyme elevations by visit
 - $> 1 \times, 2 \times, 3 \times, 5 \times, 8 \times, 10 \times, 20 \times$ upper limit of normal (ULN) elevation in ALT
 - $> 1 \times, 2 \times, 3 \times, 5 \times, 8 \times, 10 \times, 20 \times$ ULN elevation in AST
 - $> 3 \times, 5 \times, 10 \times, 20 \times$ ULN elevation in either ALT or AST
 - $> 1 \times, 1.5 \times, 2 \times, 3 \times$ ULN elevation in total bilirubin
 - $> 1 \times, 1.5 \times, 2 \times, 3 \times, 5 \times, 8 \times$ ULN elevation in ALP
 - $> 1 \times, 2 \times, 3 \times, 5 \times, 8 \times$ ULN elevation in GGT
 - $> 3 \times$ ULN elevation in either ALT or AST and $> 1.5 \times$ ULN elevation in total bilirubin
 - $> 3 \times$ ULN elevation in either ALT or AST and $> 2 \times$ ULN elevation in total bilirubin
 - $> 3 \times$ ULN elevation in either ALT or AST and $> 1.5 \times$ ULN elevation in ALP
 - $> 3 \times$ ULN elevation in either ALT or AST in temporal association with treatment-emergent nausea, vomiting, anorexia, abdominal pain, or fatigue identified by PT, where temporal association is defined as ± 14 days of onset date from the time of elevation.

If both central and local assessments of total bilirubin are available on the same day, the central result will take precedence over the local result in the eDISH plot. If the maximum AST, ALT, GGT, or ALP assessment occurs at 2 different dates, the assessment with the higher

accompanying Bilirubin value will be used. Two versions of the eDISH plots will be presented, with one showing values as multiples of ULN, and the other one showing values as multiples of ULN, or subject's baseline, whichever is higher.

Only laboratory tests completed by 50 or more subjects in the Safety Set will be presented in the summaries. All laboratory tests will be listed.

Subject's laboratory assessments at all timepoints will be listed in chronological order. Values outside of the laboratory reference range will be flagged. Values obtained from local laboratory will be flagged. A listing of lymphocytes and neutrophils over time in subjects who ever had lymphocytes $< 0.5 \times 10^9/L$ or neutrophils $< 1 \times 10^9/L$ will also be provided.

